3.1 Sample Size and randomisation

A total of 80 subjects (at 90% power) are required for recruitment into the 600 IU vitamin D group vs placebo group for the RCT to be conducted in the UK and a total of 80 subjects (at 90% power) are required for recruitment into the 600 IU vitamin D group vs. placebo group for the RCT to be conducted in Brazil. This will enable us to detect a 0.6 SD size effect at 90% power in serum 25OHD levels between placebo and 600 IU in UK-dwelling Brazilian populations and Brazilians living in Brazil. These study numbers of 40 subjects for the vitamin D group and n 40 for the placebo group includes a 20% drop-out rate factored in.

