3.0 Experimental Design

Two controlled, randomized, double-blind clinical trials will be developed and undertaken (one in Brazil and the other in the UK) with an intervention period of 12 weeks.

A questionnaire to screen for the relevant inclusion and exclusion criteria (see section A) will be administered in order to select 80 Brazilian female subjects, aged 20 to 59 years, in each of the two countries. The women selected will be randomly divided into two groups: Placebo Group and Supplemented Group, the latter will receive 600UI UI of vitamin D.

The first clinical trial will run in the UK from October 2016 to March 2017 (autumn-winter) and then the second will run in Brazil from April 2017 to September 2017 (autumn-winter). After the analysis of the effect of vitamin D supplementation compared to placebo, the results obtained in the supplemented group will also be analysed according to the genotypes for SNPs in the VDR gene.

We have chosen 12 weeks (3 months) as the supplementation period as we consider this to be ample time for 25OHD levels to rise (half-life of 25OHD is 3 weeks) and this has been demonstrated to be an effective timeframe for supplementation of vitamin D in previous studies.

We have chosen 600IU to enable the study to be relevant to the new IOM US recommendations for vitamin D, which are currently the reference document used in Brazil, even though the Brazilian nutritional table remains with the daily intake recommendation of 200 IU, which was the IOM recommendation in 1997. Compliance will be checked by compliance interviews during the trial and by empty packaging count.

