3.3.3 Withdrawal

All participants will be notified during the consenting process that they are free to withdraw from the trial at any time, without giving a reason.

Participants will be withdrawn from the trial by the Principal Investigator if:

- 1. The participant develops a medical condition or becomes pregnant either prior to entering the study or during, which may adversely affect the outcome of the study.
- 2. It is clearly demonstrated that the participant is non-compliant completing study activities and the control procedures requested of them.
- 3. A participant suffers an adverse event, which will be reviewed and recorded at each visit and at each phone call, following the immediate discontinuation of the participant during the visit, if necessary.

All data prior to subject withdrawal will be used in analysis; unless the participant specifically requests that their data is not to be used. Withdrawn participants will not be replaced as an anticipated drop-out rate of 20% has been accounted for in the recruitment targets.

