7.0 Study Evaluation and Statistical Analysis

Statistical analysis will be undertaken with support from the University of Surrey statistical department. Data will be checked for normality using appropriate testing. Appropriate parametric/non-parametric analysis will be applied.

The database will be stored and analysed using SPSS ® version 13.0.

The descriptive analysis, including mean ± standard deviation, median and lower limit and higher will be held for all quantitative variables Data will be checked for normality using appropriate testing. Appropriate parametric/non-parametric analysis will be applied. Student t test or Mann-Whitney test, depending on the distribution of data, will be applied to evaluate differences between supplemented and placebo. For analysis between Brazil and UK groups an ANOVA test will be undertaken. Linear correlation, Pearson or Spearman, will be calculated in accordance with the presence / absence of normal distribution, respectively, between vitamin D intake, sun exposure, skin pigmentation and vitamin D serum concentration. Multiple linear regression analysis will be performed to determine the variants that influence blood concentrations of vitamin D. In order to determine whether supplemental response differs between genotypes, these will be separated into wild homozygotes, heterozygotes and homozygotes for the variant. In this approach, the results will be evaluated with the test ANOVA or Kruskal-Wallis, in cases of variables with normal distribution or not, respectively. To describe the relationship between food intake aspects and features biochemical independent of energy intake, intake values of nutrients of interest will be adjusted to energy in accordance with the method. Significance considered as standard will be 5%.

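### Section 3.1 claims 90% power for 0.6 SD in each country; 40 per arm less 20% drop-out gives about 66% (unadjusted t test, two-sided 5%)

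*Combined protocol and SAP*

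**What the plan says.** Section 3.1 gives the same statement for the UK trial and the Brazil trial. For the UK: "A total of 80 subjects (at 90% power) are required for recruitment into the 600 IU vitamin D group vs placebo group". The target effect follows: "This will enable us to detect a 0.6 SD size effect at 90% power in serum 25OHD levels between placebo and 600 IU". The allowance for losses is inside the recruitment figure: "These study numbers of 40 subjects for the vitamin D group and n 40 for the placebo group includes a 20% drop-out rate factored in".

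Section 3.3.3 confirms that losses will not be made up: "Withdrawn participants will not be replaced as an anticipated drop-out rate of 20% has been accounted for in the recruitment targets".

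Section 7.0 names the test for this comparison: "Student t test or Mann-Whitney test, depending on the distribution of data, will be applied to evaluate differences between supplemented and placebo". It sets significance at 5% and does not say whether tests are one- or two-sided. Section 3.0 describes two separate randomised trials, one per country. Section 3.1 mentions no baseline adjustment, no correlation between baseline and week-12 values, and no expected difference or SD in concentration units.

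**The concern.** A standardised difference of 0.6 at 90% power and two-sided 5% normally needs about 60 evaluable participants per arm. The plan expects 32, roughly half. The sentence in section 3.1 is the only power claim for the main treatment comparison, so readers and ethics committees would rely on it.

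The practical risk lies in how a null result is read. The primary objective (section 2.1) concerns response within and between women living in the two countries. If one trial is significant and the other is not, a reader who trusts 90% power may take the null trial as evidence of no effect there, and then take the contrast as a country effect. With the power actually available, such a split is likely by chance alone.

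**Working it through.** **Inputs**

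- Standardised difference d = 0.6, stated power 90% (section 3.1).
- Recruited per arm: 40. Drop-out: 20%, already included (section 3.1), not replaced (section 3.3.3). Evaluable per arm: 40 × 0.8 = 32.
- Significance level 5%, t test or Mann-Whitney test (section 7.0). Two-sided is my assumption; one-sided results are shown as the range.

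**Attempt to reproduce the plan's figure**

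Normal approximation, evaluable n per arm:

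n = 2 × [(z₀.₉₇₅ + z₀.₉₀) / d]² = 2 × [(1.960 + 1.282) / 0.6]² = 58.4, so 59.

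The exact noncentral-t solution is 59.35, so 60 per arm. Allowing for 20% loss: 60 / 0.8 = 75 recruited per arm, 150 per country. The plan has 40 and 80. The stated figure is not reproduced.

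**Power with the plan's numbers**

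The noncentrality parameter is d × √(n/2). For n = 32 it is 0.6 × √16 = 2.40, against a two-sided critical value of t = 2.00 on 62 degrees of freedom.

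| Evaluable per arm | Two-sided 5% | One-sided 5% |
|---|---|---|
| 32 (planned losses) | 65.6% | 76.7% |
| 40 (no losses) | 75.5% | 84.5% |
| 64 (both countries combined) | 92.0% | 95.8% |

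The normal approximation gives 67.0% at 32 per arm. The Mann-Whitney test, at its efficiency of 0.955 for normal data, gives about 65%. Even the most favourable single-country reading, one-sided with no losses, falls short of 90%.

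**Detectable difference at 32 per arm (two-sided 5%, t test)**

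- 90% power: 0.82 SD
- 80% power: 0.71 SD

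**Other routes to 90%**

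- *Baseline-adjusted analysis (ANCOVA).* The effective difference is 0.6 / √(1 − r²) with 61 degrees of freedom, where r is the correlation between baseline and week 12. Power is 78% at r = 0.5, 84% at r = 0.6 and 91% at r = 0.7. It reaches 90% at r = 0.685.
- *Change from baseline.* If 0.6 SD refers to the SD of a single 25OHD measurement, the effective difference is 0.6 / √(2(1 − r)). Power is 66% at r = 0.5 and 86% at r = 0.7. It reaches 90% at about r = 0.73. If 0.6 SD already refers to the SD of change, power is again 65.6%.
- *One-sample or paired formula.* This gives n = 31.2, or 31.2 / 0.8 = 39 after drop-out, with 90.8% power at 32. It comes close to the plan's 40 per arm and may be how that number arose, but the documents do not say so. It does not apply to a comparison between two independent arms.

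**Consequence across the two trials**

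If the true effect is 0.6 SD in both countries, both trials are significant with probability 0.656² = 43%, and exactly one with probability 2 × 0.656 × 0.344 = 45%. With 90% power in each, the first figure would be 0.9² = 81%.

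**The case against.** The strongest defence is that the analysis might use baseline values. The primary objective is framed as response, 25OHD is measured at baseline and at the final visit, and section 7.0 does not say whether the t test is applied to final values or to change. A well-correlated baseline could bring 32 per arm up to 90%. This stands as a possibility and limits the finding to the inputs the plan states. It does not support the sentence as written. The required correlation (about 0.69 for ANCOVA, 0.73 for change) appears nowhere, section 3.1 speaks of serum levels, and the multiple regression in section 7.0 is for determinants of vitamin D concentration, not for the sample size.

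The plan does not state sidedness, so 66% depends on assuming two-sided tests. A one-sided test raises it only to 77%.

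Combining countries does give 92%, and section 7.0 mentions an ANOVA between the Brazil and UK groups. But section 3.1 attaches 90% to each trial by name, and the ANOVA is not described as a treatment comparison combined over countries.

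Section 3.3.3 keeps data collected before withdrawal. That does not recover power, because blood is taken only at the two visits and a woman who leaves early has no week-12 value.

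The plan never requires both trials to be significant, so the 43% and 45% illustrate the risk and do not contradict a stated criterion. The treatment estimate and the type I error rate are unaffected. If the true effect is 0.82 SD or more, each trial has at least 90% power, but 0.6 SD is the effect the plan chose.

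**Conclusion.** The concern holds. On the plan's own effect size, drop-out rate and test, power per country is about 66%, some 24 percentage points below the stated 90%. This assumes an unadjusted two-sample t test at two-sided 5% with 32 evaluable women per arm. Varying sidedness and drop-out moves the figure between 66% and 85%. Only a combined analysis, or a baseline correlation the plan does not state, reaches 90%. As the sole power statement for the main comparison, the sentence must be corrected.

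**What to change.** 1. Replace the power statement in section 3.1 with wording such as:

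> With 32 evaluable women per arm, each country's trial has about 66% power to detect 0.6 SD, and 90% power to detect 0.82 SD, using an unadjusted t test at two-sided 5%.

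2. State in section 7.0 that tests are two-sided, and whether the supplemented-versus-placebo comparison uses final values, change from baseline or a baseline-adjusted model.

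3. Pre-specify a treatment comparison combined over both countries and adjusted for country. With 64 against 64 it has 92% power if the effect is 0.6 SD in both. It does not restore the per-country claim or power the comparison between countries. Section 4.1 describes the baseline scans in the past tense, so if data collection has begun, this analysis should be fixed and dated before unblinding.

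4. If ANCOVA is adopted and 90% per country is still claimed, state the assumed baseline-to-week-12 correlation and its source. It must be about 0.69 or higher.

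The cost is revised wording in sections 3.1 and 7.0, one added analysis and a less favourable per-country power figure. No extra participants are needed. Keeping 90% per country with the unadjusted test would instead require 150 women per country, 70 more than planned in each.

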2.3 Hypothesis

The study hypothesis that, during winter, vitamin D supplementation is required to obtain Vitamin D optimal levels in Brazilian women residing in the UK as well as Brazilian women residing in Brazil and that this response is dependent on the initial levels, being also influenced by sunlight exposure, skin pigmentation and polymorphisms of the vitamin D receptor gene.

H1: Dietary intakes of vitamin D are too low and sunlight exposure is insufficient for optimal vitamin D status in Brazilians living in the UK and Brazilians living in Brazil.

H2: The response of subjects to vitamin D supplementation is dependent on baseline 25OHD levels.

H3: Response to supplementation is influenced by sun light exposure.

H4: Skin pigmentation is an influential factor on vitamin D optimal levels.

H5: There will be strong genetic influences on 25OHD changes in response to vitamin D supplementation; these will be similar in both groups.

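### Power is stated per country, and section 7.0 specifies neither a country-stratified arm comparison nor an arm-by-country contrast, so a split result would be likely and hard to interpret

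*Combined protocol and SAP*

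**What the plan says.** Section 3.0 sets up two separate trials: "Two controlled, randomized, double-blind clinical trials will be developed and undertaken (one in Brazil and the other in the UK". Section 3.1 sizes each one alone. For the UK it says "A total of 80 subjects (at 90% power) are required for recruitment into the 600 IU vitamin D group vs placebo group", and it repeats the same number and power for Brazil. The effect size is given once for both: "This will enable us to detect a 0.6 SD size effect at 90% power in serum 25OHD levels between placebo and 600 IU". The arms are "These study numbers of 40 subjects for the vitamin D group and n 40 for the placebo group", a figure that "includes a 20% drop-out rate factored in".

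The primary objective (2.1) is to examine the response to supplementation inside each of the two populations and across them. The study hypothesis (2.3) covers both countries, "in Brazilian women residing in the UK as well as Brazilian women residing in Brazil", and is worded in terms of reaching optimal vitamin D levels in winter.

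For the arm comparison, section 7.0 says: "Student t test or Mann-Whitney test, depending on the distribution of data, will be applied to evaluate differences between supplemented and placebo". It does not say whether this is done by country or on both trials together. An ANOVA is named for the comparison of Brazil and the UK, and a multiple regression for influences on vitamin D concentration. The factors and covariates of both are left open. The significance level is given as "Significance considered as standard will be 5"%, without sidedness.

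**The concern.** Two independent trials, each with moderate power, can easily give one significant and one non-significant result when the true effect is the same in both countries. Because the primary objective asks about response across the two populations, such a split invites the reading that supplementation works in one country and not in the other. Two separate arm tests cannot tell that apart from chance. A contrast of the two arm effects can, and section 7.0 does not specify one.

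The background section stresses that the two trials follow the same design, so an arm comparison across both, with country as a stratum, is a natural analysis of data that will already exist. Without it, the study reports two tests of limited power and no estimate from all the randomised women.

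**Working it through.** **Inputs**
- Effect: 0.6 SD, placebo versus 600 IU (3.1).
- Recruited: 40 per arm per country (3.1).
- Drop-out: 20%, already included (3.1), so completers are 40 × 0.80 = 32 per arm. Withdrawn women are not replaced (3.3.3), and blood is taken only at baseline and at the final visit (4.1).
- Significance level: 5% (7.0), taken here as two-sided.
- Test: two-sample t test (7.0), with no baseline adjustment, since none is stated.
- The trials recruit different women, so their results are independent.

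**Step 1: the plan's own 90%.** Power comes from the noncentral t distribution with 2n − 2 degrees of freedom and noncentrality 0.6 × √(n/2).
- n = 32: 0.6 × √16 = 2.40, power 65.6% (normal approximation 67.0%).
- n = 40, no drop-out: 0.6 × √20 = 2.68, power 75.5% (normal approximation 76.5%).
- One-sided 5%: 77% at n = 32 and 85% (normal approximation 85.0%, t 84.5%) at n = 40.

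None of these reaches 90%. A two-sided 90% needs 59 completers per arm by the normal approximation (60 by the t distribution). With 20% drop-out that is 59/0.80, or 74 recruited per arm, against the planned 40. A one-sample or paired t test with 32 women does give 90.8%, and 32/0.80 = 40, but that is not the between-arm comparison which section 3.1 names.

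**Step 2: how often the two trials agree.** With power p in each trial, both are positive with probability p², exactly one with 2p(1 − p), and neither with (1 − p)².

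| Basis | p | Both | Exactly one | Neither |
|---|---|---|---|---|
| Printed power | 0.90 | 0.81 | 0.18 | 0.01 |
| 40 per arm, no drop-out | 0.755 | 0.570 | 0.370 | 0.060 |
| 32 completers per arm | 0.656 | 0.431 | 0.451 | 0.118 |

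At the planned completers, a split result is about as likely as two positive trials, although the true effects are equal.

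**Step 3: one arm comparison stratified by country.** Completers across both trials are 2 × 32 = 64 per arm. Noncentrality is 0.6 × √(64/2) = 3.39, which gives 92.0% power. With no drop-out (80 per arm) it is 96.5%. Both figures use the within-country SD and assume a common 0.6 SD effect. The one degree of freedom spent on country is negligible.

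**Step 4: precision of the arm-by-country contrast.** It is the difference between two arm effects and so has four group means of 32. Its standard error is SD × √(4/32) = 0.354 SD, and the 95% half-width is about 1.96 × 0.354 = 0.69 SD. That is wider than the planned effect itself.

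**The case against.** **No joint success rule.** A reader might infer that power for the study's conclusion is at most 0.90 × 0.90 = 81%, because the hypothesis covers both countries. The documents do not support that. No section requires both trials to be significant, and sizing and concluding two trials separately is legitimate. The hypothesis in 2.3 is about reaching optimal levels, whereas section 3.1 powers a mean difference between arms. And 81% is a ceiling only if the true effect is no larger than 0.6 SD in each country. This objection stands, and the figures in the table are to be read as the risk of a split result only.

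**The low figures come from another defect.** The fall from 81% to 43% arises because 32 per arm does not deliver 90% per trial. That is correct. At a true 90% the split risk is 18%, which is smaller but not negligible.

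**The ANOVA or regression may already contain arm and country.** This is possible, since neither has stated factors. The accurate statement is that no such analysis is specified, and it would be wrong to say that the plan excludes one.

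**A combined estimate does not answer the question by country.** One country could drive it, and H3 expects response to depend on sunlight, so a common effect is not the plan's own expectation. This also stands. It is why the interaction must accompany the combined estimate and why neither replaces the country-specific results.

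**Nothing says that a split would be misread.** This is true, but nothing in section 7.0 states how it would be read either.

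**Conclusion.** The concern holds as a gap in specification. Section 3.1 gives power for each country alone, and section 7.0 specifies neither an arm comparison across both trials with country as a stratum nor a contrast of the arm effects between countries, which the across-population part of the primary objective needs.

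With a true 0.6 SD effect in each country, 32 completers per arm and two-sided unadjusted t tests at 5%, each trial has about 66% power, both are positive about 43% of the time, and exactly one about 45%.

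These sizes depend on the assumptions. A larger true effect or a one-sided test would raise the power. So would adjustment for baseline, which the plan does not specify for this comparison: as an assumption, a baseline-to-final correlation of about 0.67 would be needed to bring each trial to 90% with 32 per arm.

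**What to change.** 1. **Section 7.0, combined analysis.** Add one linear model of 12-week serum 25OHD on arm and country, as a supplementary analysis of both trials.
2. **Section 7.0, country contrast.** Add the arm-by-country interaction with its confidence interval, and report it and the combined estimate beside the two country-specific estimates and their intervals. State that any claim of a country difference in response will rest on the interaction, and not on significance in one country only.
3. **Section 3.1.** Say that the power is per country, and restate it at what the planned completers deliver: about 66% for 0.6 SD with 32 per arm, two-sided 5%.

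The cost is some wording in 3.1 and one model with its interaction in 7.0, with no extra participants or measurements. The downsides are that the combined estimate averages over countries whose responses may differ (H3), and that the interaction will be imprecise (half-width about 0.7 SD). A wide interval that includes zero must therefore not be reported as showing equal response.

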3.2 Recruitment

Participants in the UK will be recruited through advertisement among local Brazilian societies/groups within Surrey and London. Informative posters will be positioned around the University of Surrey and commercial centres (with a focus on Brazilian themed places), with permission of the owner.

As recruitment method, we will ask, after clearly explaining our intentions of divulgating the study, Brazilian institutions in the UK, such as the Brazilian Consulate and the Brazilian Researchers Association (ABEP-UK) to circulate a recruitment letter to their contact list of Brazilians living in the UK. If we succeed in this arrangement, this letter will be send directly to those in the lists by the institution, therefore we will not need to have access to people's contact details.

Social media sites such as Facebook will be used to publicise the study: the poster or flyer will be inserted as a photo with permission of the administrator of the Facebook pages. Facebook pages we intend to target :

Science Without Borders UK students: https://www.facebook.com/groups/489494047812445/ and https://www.facebook.com/groups/csf2014/

Brazilians in London: https://www.facebook.com/groups/301278086667948/

Brazilian Students in the UK Association (ABEP): https://www.facebook.com/ABEPUK/?fref=ts General Consulate of Brazil in London: https://www.facebook.com/cglondres/info/

Participants in Brazil will be recruited from the general public within the city of Goiânia through posters to be positioned around the Federal University of Goiás and commercial centres, with permission of the owner.

Social media sites such as Facebook will be used to publicise the study: the poster or flyer will be inserted as a photo with permission of the administrator of the Facebook pages. Facebook pages we intend to target:

Federal University of Goias: https://www.facebook.com/universidadefederaldegoias/?fref=ts Faculty of Nutrition, Federal Uni of Goias: https://www.facebook.com/fanut.ufg.5?fref=ts Faculty of Nutrition Postgrads, Federal Uni of Goias: https://www.facebook.com/mestrado.fanut.7?fref=ts

The recruitment end date for the UK subjects will be 14th December 2016. Recruitment end date for the Brazilian subjects will be the 13th June 2017.

Subjects will be reimbursed for their travel expenses.

